3.1.3. Analysis of exploratory outcomes

For the exploratory outcomes, we will report only descriptive statistics specified in section 2.6.

3.1.4. Dose-response analysis

A dose-response analysis will be used to test usage as a mediator of each outcome. Multiple measurements of usage were collected and are listed in Appendix A. Metrics specified in section 2.3 will be created by assessing whether the participant used any app activity on a given day. Logging into the app without activity will not count as app usage because this information was not collected for the full study period. Activity use is also more likely to be associated with engagement with the app than is login alone. Daily usage and weekly usage will be the dependent variables for the dose-response models. As an exploratory analysis, the PCI may be analyzed as a dependent variable. The dose-response relationship will be analyzed for the primary and secondary outcomes using a multiple linear effects model and the confounder adjustment method (12). The model for adherence will be created using 20% of the unblinded data. The dose-response effects for the primary outcome will be reported in the manuscript. The dose-response effect for the secondary outcomes will be reported in the supplemental material.

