2.3. Treatment Usage

At its current stage of development, the MHP app does not prescribe a set dosage, specifying how often patients should interact with it in order to have desired effects. As such, this study investigates app usage as a mediator of the outcome, rather than comparing users who did and did not meet a predetermined dosage.

We will assess the following aspects of usage: how soon after receiving the prescription participants initiated app use (in days); how soon they discontinued app use prior to delivery (in days since initiation); the percentage of days they used it overall (within the usage period); and the percentage of weeks they used it at least once (within the usage period). See Appendix A for details on these use metrics.

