EST_GEST_AGE_DAYS	gestational age at the time of birth	Primary outcome
MOM_DELIVERY_WT	weight of mother at time of delivery (kg)	Secondary outcome
PREGANY_DEPRESSION	Diagnosis of depression or active depression at some point during pregnancy (would also be 1 if PREGSTART_DEPRESSION is 1) (binary variable)	Secondary outcome
PREGANY_ANXIETY	Diagnosis of anxiety or active anxiety at some point during pregnancy (would also be 1 if PREGSTART_ANXIETY is 1) (binary variable)	Secondary outcome
PREGANY_PREE	Preeclampsia diagnosed or listed as active problem at any visit while pregnant (binary variable)	Secondary outcome
PNV_COUNT	Number of prenatal appointments attended	Secondary outcome
PNV_TOTSCHED	Number of prenatal appointments scheduled (blank if the same as PNV_COUNT i.e. they didn't cancel any appointments)	Secondary outcome
PREGANY_BEHAVIORALREF	Behavioral health referral at some point during pregnancy (binary variable)	Secondary outcome
PREGANY_SWREF	Social work referral at some point during pregnancy (binary variable)	Secondary outcome
BABY_DISPOSITION	baby's disposition after birth (home health agency, home/self care, children's hospital, cease to breathe, etc)	Exploratory outcome
STILLBORN	whether this baby was stillborn (binary variable)	Exploratory outcome
C_SECTION	Had c-section (binary variable)	Exploratory outcome
BIRTH_WEIGHT	baby's birth weight in grams	Exploratory outcome
NICU_DELIVERYADMISSION	whether the baby was brought to the NICU (binary variable)	Exploratory outcome
ASSUMED_INDUCTION	If a delivery was by c-section prior to 259 days gestation, but there is no documentation of induction then we assume	Exploratory outcome

	it was indicated and this column has a 1 (binary variable). Otherwise, it's 0. Definition came from Hy.	
INDICATED_ONSET	When a delivery form documents that a delivery was induced but not for PROM (binary variable). Definition came from Hy.	Exploratory outcome
CURRENT_PPROM	premature rupture of membranes; diagnosis of O42* during current delivery (binary variable).	Exploratory outcome
VISITNUMBER_F2F	Number of face-to-face visits when pregnant.	Exploratory outcome
PREGANY_PREGINDUCEDHTN_NOPROT	Gestational hypertension without significant proteinuria, could occur during any trimester, childbirth, or puerperium; Diagnosed or listed as active problem at any visit while pregnant. Definition came from EPIC codes	Exploratory outcome

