PREGANY_SUPERIMPPREE	Superimposed Preeclampsia diagnosed or listed as active problem at any visit while pregnant (binary variable)	Exploratory outcome
PREGANY_ECLAMPSIA	Eclampsia diagnosed or listed as active problem at any visit while pregnant (binary variable)	Exploratory outcome
PREGANY_UNSPHTN	Unspecified hypertension diagnosed or listed as active problem at any visit while pregnant (binary variable)	Exploratory outcome
PREGANY_ANYHTN	Any hypertension diagnosed or listed as active problem at any visit while pregnant (binary variable)	Exploratory outcome
PREGANY_GDM	Gestational diabetes diagnosed or listed as active problem at any visit while pregnant (binary variable)	Exploratory outcome
CANCELEDVISIT_COUNT	Number of prenatal appointments canceled (blank if 0 appointments canceled)	Exploratory outcome
ANTEPARTUM_EDLD	Number of EDLD visits during pregnancy (EDLD = Emergency Department Labor and Delivery)	Exploratory outcome
ANTEPARTUM_EDTR	Number of ER visits during pregnancy	Exploratory outcome
ANTEPARTUM_ADMISSION	Number of 'IP' or 'OP' hospital visits between pregnancy start date in Epic and delivery	Exploratory outcome
ANTEPARTUM_LOS	Sum of all antepartum admission lengths of stays for each delivery.	Exploratory outcome
POSTPARTUM_EDTR	Number of postpartum visits to ER up to 42 days after pregnancy	Exploratory outcome
POSTPARTUM_ADMISSION	Number of 'IP' or 'OP' hospital visits between delivery date and 42 days postpartum.	Exploratory outcome
POSTPARTUM_LOS	Sum of all postpartum admission between delivery date and 42 days postpartum.	Exploratory outcome
POSTPARTUM_NICU	Provided flags for infant ICU admission within 42 days postpartum.	Exploratory outcome
PP_LOS	postpartum length of stay in hospital in days	Exploratory outcome

Usage metrics

Variable Name	Description
DailyCheckin	Dates of filling out the daily check-in (includes responses to questions on daily mood, number of hours slept, sleep quality, SDOH questions, aspirin adherence, etc)
ArticleReads	Dates of clicking on any article within the app (only after November 2020)
MentalHealthCheckin	Dates of filling out mental health check-in
RelationshipHealthCheckin	Dates of filling out relationship health check-in
SleepHealthCheckin	Dates of filling out sleep health check-in
HelpfulResource	Dates of looking at the helpful resource section (only after November 2020)
HelpfulResourceClick	Dates of clicking on a helpful resource from the helpful resources section (only after November 2020)

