OpensApp	Dates of accessing the app at all (best after November 2020, but can also seem many things before November 2020)
Kick Counter	Dates of logging a kick-counting session in Kick Counter section of the app
Contraction Counter	Dates of logging contractions in the Contraction Counter section of the app
Journaling Section (just dates)	Dates of entering a journal into the journaling section of the app
Adding appointment reminders	Dates of adding in an appointment into the Prenatal Visits section of the app

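### Dose-response models for seven secondary outcomes count app use that the outcome may itself prompt, so a slope can arise with no app effect

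*SAP*

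**What the plan says.** Section 3.1.4 of the SAP sets out dose-response models for the primary and all secondary outcomes and describes usage as a mediator. The dose is built the same way for each outcome: "Metrics specified in section 2.3 will be created by assessing whether the participant used any app activity on a given day". The only exclusion is a login without activity. Section 2.3 defines daily use as "the percentage of days they used it overall (within the usage period"), and weekly use in the same way. Neither is cut off at the date of the outcome.

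The usage metrics in Appendix A include *Adding appointment reminders* ("Dates of adding in an appointment into the Prenatal Visits section of the app") and the mental health check-in ("Dates of filling out mental health check-in").

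The outcomes concerned are also in Appendix A. Outcome 8 is a total, "Number of prenatal appointments attended". Outcomes 2 to 6 (depression, anxiety, two kinds of referral, preeclampsia) are yes/no flags for the pregnancy as a whole. The depression flag, for example, is "Diagnosis of depression or active depression at some point during pregnancy". No event dates are listed.

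Section 3.1.1 limits candidate confounders to baseline variables. Section 3.1.2 finds no literature confounders for referrals or appointments. Secondary dose-response results go to the supplement.

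**The concern.** A mediator has to come before the outcome it is meant to explain. The plan does not secure that order for seven of the nine secondary outcomes.

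- **Appointments (outcomes 8 and 9).** A woman with more scheduled visits has more to enter in the app. Each entry can turn an unused day or week into a used one, so the schedule behind the outcome helps to create the dose.
- **Diagnoses and referrals (outcomes 2 to 6).** Use after the event counts as dose for an event it cannot have affected. If the event makes a woman use the app more or less, that change appears as a slope.

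Both links arise after baseline, so adjusting for baseline confounders does not remove them. The supplement could then present use driven by the outcome as an effect of the app. Preterm birth (outcome 1) and weight gain (outcome 7) are not part of this point.

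**Working it through.** **The plan's own figure.** The SAP's only power statement (section 1.5) concerns the cohort comparison: (1.960 + 0.842) × √(1/7147 + 1/5197) = 2.802 × 0.01823 = 0.051 SD. With an SD of 10 days this is 0.51 day, so the figure reproduces. The SAP gives no such figure for the dose-response models.

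**Inputs.** From the SAP: an MHP cohort of 5,197 or 7,147 (which one is blinded) and a 5% level, taken as two-sided. Everything about behaviour below is an assumption.

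**Appointment entries, simulated with no app effect.** n = 5,197; 196-day usage period; visits Poisson with mean 11, independent of use; each visit entered in the app with probability q on a random day; linear regression with robust standard errors; 60 replicates per cell. False rejection, daily / weekly dose:

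| q | mean daily use 10% | mean daily use 25% |
|---|---|---|
| 0 | 8% / 7% | 0% / 3% |
| 0.10 | 17% / 40% | 7% / 15% |
| 0.25 | 57% / 98% | 20% / 55% |
| 0.50 | 98% / 100% | 57% / 98% |

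At q = 0.50 the slopes per 10 points of use are 0.15 (daily) and 0.13 (weekly) visits at 10% mean use, and 0.05 and 0.07 at 25%. With entries left out of the dose, rejection is 0 to 8% in all cells and slopes are about zero.

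**Use after an event, simulated with no app effect.** Same n and period; mean daily use 25%; event at a uniformly random time; daily use multiplied by r afterwards. False rejection, daily / weekly dose:

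| r | prevalence 5% | prevalence 20% |
|---|---|---|
| 0.75 | 70% / 40% | 100% / 92% |
| 1.00 | 7% / 5% | 8% / 5% |
| 1.10 | 22% / 20% | 35% / 22% |
| 1.25 | 63% / 40% | 97% / 70% |
| 1.50 | 97% / 60% | 100% / 98% |

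At 20% prevalence the daily slope runs from −1.3 (r = 0.75) to +2.3 (r = 1.50) percentage points of outcome per 10 points of use. With the dose taken from the first 8 weeks, among women event-free at that point, rejection is 2 to 13% across the 20 cells (mostly 5 to 8%) and slopes are about zero. The Monte Carlo standard error at a true 5% is √(0.05 × 0.95/60), about 3 points.

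**How far timing matters.** Let use be 12% of days with SD 12 points, a share p have the event, use fall by a fraction f afterwards, and a fraction g of the usage period remain after the event. Then z = f × g × √(N p (1 − p)).

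- Uniform timing, g = 0.5: from 0.20 × 0.5 × √(5197 × 0.10 × 0.90) = 2.2 to 0.30 × 0.5 × √(7147 × 0.15 × 0.85) = 4.5. The probability of p < 0.05 is 0.58 to 0.99.
- Late events, g = 0.1 to 0.2: from 0.20 × 0.1 × 21.6 = 0.4 to 0.30 × 0.2 × 30.2 = 1.8. The probability is about 0.07 to 0.44.

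**The case against.** Several points on the other side stand.

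- **The slope is conditional.** A reader might infer that a false slope must appear. The SAP does not support that: it gives no entry rates, event timing or post-event behaviour. With no entries or no change in use, rejection is near nominal.
- **Entries do not record the outcome.** A reader might take an appointment entry as a log of attendance. Appendix A labels the activity as adding reminders, so it reflects planned visits. The link to the number attended (outcome 8) is indirect but plausible. For the proportion attended (outcome 9), more scheduled visits need not mean a higher proportion, so the direction is open.
- **Reminders may be part of the treatment.** Section 1.4.2 says the secondary measures are ones that app components are meant to affect. Dropping reminders outright could hide a real effect on attendance.
- **Prevalent cases.** The depression and anxiety flags include conditions present at the first visit, and section 3.1.2 adjusts for history of both. That deals with prevalent cases but not new ones.
- **Usage period.** Section 2.3 does not say when it ends. If it ends at last use, stopping the app altogether after an event does not dilute the percentages. Changed use before stopping still counts.
- **Significance is not size.** With more than 5,000 women, small slopes reach p < 0.05. If the nine-fold Bonferroni correction in section 3.1 also covers these models, which is not stated, the range 0.58 to 0.99 becomes 0.27 to 0.96.

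These points limit the size and certainty of the problem. None of them restores the time order that a mediation analysis needs.

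**Conclusion.** The point holds as a possible bias, not a demonstrated one. The SAP fixes a dose that includes appointment entries and use after the event, applies it to outcomes 2 to 6, 8 and 9, and plans only baseline adjustment. A slope of either sign can therefore arise with no app effect.

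Under the assumptions shown, false rejection runs from near 5% to above 90%. In the cases run, the slopes reach at most about 0.15 visit, or about 2.3 percentage points of outcome, per 10 points of use. Entry rates, mean use, prevalence, timing and change in use are all assumed, and late events shrink the problem considerably.

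The documents do not support the inference that the main results are affected. The cohort comparisons for the primary and secondary outcomes do not use this dose, and the secondary dose-response results are supplementary. What is at risk is how those supplementary slopes are read.

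**What to change.** Change section 3.1.4 as follows.

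- **Outcomes 8 and 9.** Report the daily and weekly models twice, with and without *Adding appointment reminders* in the dose. State in advance that a slope which disappears without it will not be read as an app effect.
- **Outcomes 2 to 6.** Take the dose from a fixed early window. Analyse events first recorded after that window, among women event-free at its end, using first-entry dates from the EHR. If those dates cannot be obtained, report the slopes as associations that may reflect use following the outcome, not as dose-response or mediation effects.

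Section 3.1.4 also calls daily and weekly usage the dependent variables of these models. That should be reconciled with their role as the dose.

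The cost is one extra derived usage variable (usage is already held as dates by activity) and a request for event dates. For outcomes 2 to 6 there will be fewer events and wider intervals, use after the early window is not counted, and the question narrows to events arising after it.

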A Blinded Evaluation of the Effectiveness and Efficacy of the MyHealthyPregnancy Application Statistical Analysis Plan

This study will evaluate the effectiveness and efficacy of the MyHealthyPregnancy App, an app designed to reduce preterm birth risk. This study will use observational cohort data collected at the University of Pittsburgh Medical Center between September of 2019 and February of 2022.

July 18, 2022

[name], [name]

1. Description of the study

MyHealthyPregnancy (MHP) was developed using decision science principles to help prevent preterm birth. An observational cohort trial was conducted at the University of Pittsburgh Medical Center starting in September of 2019 until February 2022. This trial compares the effectiveness of MHP to usual care for pregnant people who delivered at the University of Pittsburgh Medical Center (UPMC). Patients at UPMC were able to download the MHP app after receiving a prescription for the app, as indicated by an EHR variable. Those who were prescribed the app and downloaded it were in the *MHP cohort*. Those who were prescribed the app and did not download it were in the *usual care cohort*. Prescriptions were offered to pregnant people by their care team at an early prenatal visit at UPMC.

EHR data is available for both cohorts of patients. It is the source of all measures, unless otherwise noted.

A linear effects model will be used to evaluate effectiveness by estimating the average treatment effect for the primary endpoint, preventing preterm birth risk.

For each dependent measure, these models will control for primary predictors, as identified in the research literature, that are available in the EHR.

A dose-response model will be used to estimate the effects of continuous measures of non-adherence (as opposed to dichotomous non-adherence, such as not initiating app use). Multiple measures of adherence will be analyzed, including measures of daily use, weekly use, time to initiation, and time from discontinuation to birth.

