1.6. Overview of proposed analyses

EG will analyze the primary, secondary, and exploratory outcomes for the trial data. LH will generate data and run models as needed so that EG remains blinded to the identity of each cohort (see section 2.5).

The primary analyses will be multiple linear regression models estimating average treatment effects of the MHP app. Secondarily, dose-response models will be created for the primary and secondary outcomes in order to understand the moderating effects of app usage.

The primary and secondary outcomes for the study will come from electronic health record (EHR) data for trial participants. Given the source and the nature of care for women who deliver in the UPMC system, few outcome data are missing data. As such, imputation will not be used to account for missing outcome data. Instead, participants will be excluded from analyses, if their outcome data is missing for an outcome measure.

As a sensitivity analysis, propensity score matching will be used to create similar cohorts of participants, excluding participants whose propensity scores are outside the overlap in the covariate distributions for the covariates that predict downloading the MHP app (see section 3.1.5). We will calculate average treatment effects for these matched subsets of participants. Inverse probability of treatment weighting will be used as an additional sensitivity analysis to account for the potential lack of overlap in covariate distributions between the study cohorts.

2. Data analysis plan – data description

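### Section 3.1.4 labels app usage as the dependent variable of the dose-response models, which contradicts the stated aim of estimating how outcomes change with usage

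*SAP*

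**What the plan says.** The SAP describes the place of app usage in five ways.

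- **Section 1 (Description of the study):** "A dose-response model will be used to estimate the effects of continuous measures of non-adherence". Usage is the exposure here. The same section applies the word dependent to the outcomes: "For each dependent measure, these models will control for primary predictors".
- **Section 1.6:** the dose-response models are built "in order to understand the moderating effects of app usage".
- **Section 2.3:** "this study investigates app usage as a mediator of the outcome". Section 3.1.4 opens in the same way: "A dose-response analysis will be used to test usage as a mediator of each outcome".
- **Section 3.1.4, on the model:** "Daily usage and weekly usage will be the dependent variables for the dose-response models". The next sentence adds: "As an exploratory analysis, the PCI may be analyzed as a dependent variable".
- **Section 3.1.4, the sentence after that:** "The dose-response relationship will be analyzed for the primary and secondary outcomes using a multiple linear effects model and the confounder adjustment method (12". The primary-outcome result then goes into the manuscript and the secondary-outcome results into the supplement.

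A separate model, with usage properly as the response, is described in section 2.5 (confounders of app usage) and named in 3.1.4 as the model for adherence. The SAP gives no equation for the dose-response model, no decomposition into direct and indirect effects, and no interaction term.

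**The concern.** A dose-response analysis should report how much the outcome changes per unit of dose. With usage on the left-hand side, gestational age at birth, which is known only at delivery, becomes a predictor of earlier app use. The coefficient is then in percentage points of use per day of gestation. For a binary secondary outcome such as preterm birth, it is the adjusted difference in mean usage between those with and without the event. Either number looks plausible in a table, but neither says how the outcome varies with use.

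The split of work in section 2.5 adds to the risk. One analyst runs the outcome models on the full data and passes the results to the blinded statistician for interpretation. The written specification therefore has to settle which variable is the response. The mediator and moderator labels do not help, since they imply different models and neither is specified.

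**Working it through.** The SAP gives no figure for the dose-response analysis, so there is nothing to reproduce on this point. Its 0.51-day detectable difference (section 1.5) concerns the cohort comparison only.

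**Step 1. What each role would require.**
- Exposure (section 1): outcome on the left, usage on the right.
- Moderator (1.6): an interaction term involving usage. None is given.
- Mediator (2.3 and 3.1.4): one model for usage, one for the outcome given usage, and a split of the effect. No split is given.
- Dependent variable (3.1.4): usage on the left.

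The first and last cannot both describe the same regression.

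**Step 2. What each direction estimates.** Let Y be gestational age in days, D usage in percentage points and C the covariates.
- Outcome as response: Y = a + b·D + c·C, where b is days per point of usage.
- Usage as response: D = a′ + b′·Y + c′·C, where b′ is points of usage per day.
- With the same C, b × b′ equals the squared partial correlation r². With ordinary standard errors, t = √[r²·df/(1 − r²)] for both. The test is the same; the estimate and interval are not.

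**Step 3. Illustration on simulated data.**

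Inputs:
- n = 7147, one of the two cohort sizes in section 1.5 (which cohort it is remains blinded)
- residual SD 10 days, borrowing the SD in section 1.5
- assumed: usage SD of 25 or 10 points
- assumed: one covariate correlated 0.4 with usage and worth 2 days per SD
- assumed: true effect of 0.05 or 0.02 day per point

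| Usage SD | True effect | Slope, outcome as response (days per point) | Slope, usage as response (points per day) | t, both directions |
|---|---|---|---|---|
| 25 | 0.05 | 0.055 | 0.279 | 10.555 |
| 25 | 0.02 | 0.0189 | 0.0999 | 3.671 |
| 10 | 0.05 | 0.0516 | 0.0419 | 3.934 |
| 10 | 0.02 | 0.0118 | 0.0098 | 0.909 |

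Check on the first row: b × b′ = 0.055 × 0.2793 = 0.01536; df = 7147 − 3 = 7144; √(0.01536 × 7144 / 0.98464) = 10.56, which agrees to rounding.

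With the outcome as response, the slope estimates the true effect up to sampling error. With usage as response, it estimates a different quantity in different units. In the third row the two numbers are close by accident of scale, so a reversed model would not be obvious from the output.

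**The case against.** The strongest reply is that the intent can be recovered. Section 1 speaks of effects of non-adherence and uses dependent for the outcomes, and two sentences after the label 3.1.4 says that the relationship is analysed for the primary and secondary outcomes. No sentence makes an outcome a predictor. The PCI sentence directly follows the first, so the repetition is weak evidence of a deliberate choice. The word may have been carried over from the adherence model, where it would be correct. All of this stands, and a slip is the likeliest explanation. It does not remove the contradiction: the label is attached to the dose-response models by name, and the adherence model is mentioned separately in the same section.

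It is also fair that a mediator is normally a response in one equation and a predictor in another, so not every role listed is incompatible with every other. The conflicts that remain are the label on the wrong model and mediator against moderator.

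Two stronger readings are tempting, but the document does not support them.

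- A reader might infer a very large error by inverting the usage-on-outcome slope and reading it as a dose effect. Nothing in the SAP proposes taking a reciprocal, and the size of such an error would only restate an assumed correlation.
- A reader might infer that the model must be fitted in the MHP cohort alone, or that the cited method cannot address mediation. The source of that method is not at hand, and an MHP-only fit would have to be squared with section 2.5, where random usage values are generated for the usual care cohort to preserve blinding.

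**Conclusion.** The point holds as a contradiction in the operative analysis section. Followed literally, 3.1.4 would put into the manuscript an estimate and confidence interval for the wrong quantity. The significance test in a linear model with the same covariates and ordinary standard errors would be unchanged. The document does not establish that the sponsor intends a reversed regression. What it establishes is that the only explicit placement of usage in the model is wrong for the stated aim, and that no equation corrects it.

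The size is limited. Section 1.6 ranks dose-response below the main analyses, and the primary and nine secondary cohort comparisons are untouched. The simulated slopes rest on assumed usage SDs, effects and covariate strength; they show the nature of the difference and do not predict its size in this study.

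**What to change.** In section 3.1.4, replace the two sentences that carry the label with wording such as:

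> Each primary or secondary outcome is the dependent variable. Daily usage, and in a separate model weekly usage, is the exposure; the PCI, if analysed, enters in the same way. Usage is the response only in the adherence model of section 2.5.

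In addition:

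- Write out the model equation, and confirm that it agrees with the cited confounder adjustment method.
- Use one term for the role of usage in 1.6, 2.3 and 3.1.4. If mediation or moderation is really meant, specify the decomposition or the interaction term.
- State that only the result based on the MHP cohort's real usage is interpreted, and only after unblinding, because the usual care values are randomly generated. This leaves the blinding procedure of section 2.5 in place.

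The cost is a text edit in three sections, with no new data. It should be made before the cohort labels are revealed.
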